- ① Those who did not meet the requirements of the group were found after joining the group;
- ② The patient or his legal guardian decides to withdraw from the study;
- ③ Serious adverse reactions occur, and the patients cannot tolerate them;
- ④ Serious physical diseases that may endanger the patient's life occur during the study, and the treatment should be terminated regardless of whether it is related to the study medication;
- ⑤ Those who do not use the medicine according to the study protocol, and have a follow-up period of 7 consecutive days or more than 7 days cumulatively;

⑥ Combined use of prohibited drugs or other treatment methods (including ECT, laser, cerebral circulation, brain function, etc.);

⑦ Other circumstances where the main researcher thinks it is necessary to terminate the research;

⑧ Lost to follow-up.

2. Calculation of sample size

Using (G*Power software to calculate, a 20% reduction rate for amisulpride treatment of negative symptoms is taken as the effective response, the first type of error α is 0.05, the second type of error β is 0.2, bilateral Test, the test power $1-\beta$ is 0.8. With reference to the previous literature using amisulpride to treat negative symptoms of schizophrenia, the statistical effect (effect size) is 0.98. This study conservatively estimates that the effect value is 0.8 for sample size calculation. After calculation, The required sample size is 26. According to 10% dropout, about 30 samples from the study group and 15 samples from the healthy control group are matched.

3. Methods

This study included patients with schizophrenia with dominant negative symptoms as the study group; the control group included normal healthy people with similar eating habits and ages in the same region.

1) Drug intervention method of the study group: The study group was given amisulpride tablets first. The initial dose was 50 mg/d. The doctor titrated the dose to the therapeutic amount within 1 to 2 weeks according to the patient's condition. The maximum dose was 300 mg/d, every day. Observe for 8 weeks. Instructions for the patient's use of other drugs: ① It is forbidden to use other antipsychotics, anti-anxiety drugs, other antidepressants or drugs that act on the

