- 6) Other items: The two groups monitored Body Mass Index (BMI), abdominal circumference, heart rate, blood pressure, smoking and drinking, and psychoactive substance use before treatment and at the end of 2, 4, and 8 treatment.
- 7) Effectiveness evaluation index: The main evaluation index is the difference between the change of the intestinal microbial flora of the study group and the control group before and after treatment; the secondary evaluation index is the PANSS negative symptom scale score reduction rate $\geq 20\%$ as the effective group, observe the effective group and the ineffective group The difference in the changes of the intestinal microflora of the group; the correlation between the changes of the intestinal microflora of the effective group and immune factors and negative symptoms.

4. Statistical analysis

This experiment used SPSS19.0 software for statistical analysis. The measurement data adopts the mean \pm standard deviation, and the counting data adopts the rate or percentage. One-way analysis of variance was used to compare the two groups at baseline. The comparison of the study group before and after treatment used repeated measures analysis of variance. Changes in negative

symptoms, changes in immune factors and changes in intestinal flora composition were analyzed by PEARSON or SPEARMAN.

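### Both secondary indices hang on a 20% cut in PANSS negative reduction, and item 7 confines to responders a correlation that section 4 lists without restriction

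*Combined protocol and SAP*

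**What the plan says.** Section 3, item 7 names flora change in the study group against the control group as the main index. The secondary index takes "PANSS negative symptom scale score reduction rate $\geq 20\%$ as the effective group" and has two parts:

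- The plan will "observe the effective group and the ineffective group The difference in the changes of the intestinal microflora", that is, compare flora change between patients above and below the cut.
- It will correlate flora change with immune factors and with negative symptoms. On the natural reading of the sentence, this is done in the effective group only.

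Section 4 lists Pearson or Spearman analysis of the changes in negative symptoms, immune factors and flora composition. It states no population and does not mention responders.

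Section 2 uses the same 20% reduction as its definition of response, but gives neither the share of patients expected to reach it nor the expected size of either group. On numbers it says: "The required sample size is 26" and "According to 10% dropout, about 30 samples from the study group and 15 samples from the healthy control group are matched".

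**The concern.** PANSS negative score and stool are both collected at baseline and weeks 2, 4 and 8, so improvement is available as a graded measure. After the cut, a patient at 19% and one at 21% count as opposites, while 21% and 60% count as the same. In a sample of this size the loss is costly, and the balance of the two groups is left to chance.

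The second part compounds the problem. Confining the correlation to responders drops the patients who improved least and narrows the range of improvement, which pulls the correlation towards zero.

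If item 7 governs, no planned analysis relates flora change to graded improvement across all treated patients. That link is the one the study's title points to.

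**Working it through.** **The plan's own figure.** Section 2 gives "the first type of error α is 0.05", "bilateral Test", "the second type of error β is 0.2" and "This study conservatively estimates that the effect value is 0.8 for sample size calculation". An independent two-sample t-test with these inputs needs 25.5, so 26 per group (power 0.807). A paired t-test would need 15. The stated 26 thus reproduces as a per-group figure for two equal groups. Allowing for dropout, 26 / 0.9 = 28.9, in line with about 30. The calculation was not made for responders against non-responders.

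**Evaluable patients.** 30 × 0.9 = 27.

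**Information kept by a cut.** If improvement is normal and linearly related to flora change, and a share p responds, the split keeps φ(z)² / [p(1 − p)], where z is the p-quantile of the standard normal.

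- p = 0.5: 0.3989² / 0.25 = 0.637
- p = 0.7: 0.3477² / 0.21 = 0.576
- p = 0.8: 0.2800² / 0.16 = 0.490
- p = 0.9: 0.1755² / 0.09 = 0.342

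The formula is symmetric in p. Below 50% response the same losses apply, and the effective group becomes the smaller one.

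**Power at n = 27, true r = 0.5, two-sided 0.05.** In simulation (20,000 replicates) a Pearson test on the continuous score in all patients has power 0.78. The Fisher approximation agrees closely: 0.549 × √24 − 1.96 = 0.73, so power is about 0.77. For the analyses that depend on the cut:

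| Share responding | Ineffective group of 27 | Information kept | Power of split | Responder-only r, average | Responder-only power |
|---|---|---|---|---|---|
| 50% | 13–14 | 64% | 0.57 | 0.31 | 0.20 |
| 70% | 8 | 58% | 0.51 | 0.36 | 0.36 |
| 80% | 5 | 49% | 0.44 | 0.39 | 0.47 |
| 90% | 3 | 34% | not run | not run | not run |

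Other simulation runs agree to within about 0.01.

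**Check on the responder-only correlation.** At 50% response the variance of improvement among responders falls to 1 − 0.637 = 0.363 of its full value. The correlation becomes 0.5 × √0.363 / √(0.25 × 0.363 + 0.75) = 0.301 / 0.917 = 0.33, close to the simulated average of 0.31 in about 13 patients.

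**Other true correlations.** The documents give none, so r = 0.5 is only one point in a range.

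| True r | Continuous, all patients | Split, 50% to 80% response |
|---|---|---|
| 0.3 | 0.33 | 0.23 to 0.17 |
| 0.4 | 0.56 | 0.37 to 0.29 |
| 0.5 | 0.78 | 0.57 to 0.44 |
| 0.7 | 0.99 | 0.92 to 0.77 |

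The split loses at every value tried. At r = 0.3 neither analysis is adequate.

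**The split on section 2's own scale.** For a standardised difference of 0.8 between the two groups, power is 52% at 13 against 14 (detectable difference at 80% power: 1.12), 45% with 8 ineffective patients (1.23), 34% with 5 (1.44) and 24% with 3 (1.79).

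**The case against.** The strongest reply is that section 4 already lists the continuous analysis. The Pearson test with power 0.78 is one the plan names, so a reader who infers that the plan as a whole discards a third to a half of its information goes too far; the loss belongs to the effective/ineffective comparison. That stands. It does not settle the matter, because item 7 is the only place that states a population for the correlation, and it states responders.

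Other stronger readings are tempting and also fail.

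- *The ineffective group will have 5 to 8 patients.* That needs 70% to 81% response, and the documents give no rate.
- *The baselines go unused.* They enter the percentage reduction and the flora change. They are only not used as covariates.
- *A baseline-adjusted regression would have power 0.78, or would save a known share of variance.* The 0.78 belongs to a simple correlation. The usual saving from adjustment assumes equal variances at both visits, and it is not assured when improvement is not randomised, since adjusted and change-score analyses may then answer different questions.

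It is also fair to say that a prespecified responder comparison beside a correlation is common practice, that the cut matches section 2's response definition, and that these are secondary indices. That limits the weight of the point and does not remove it.

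**Conclusion.** The point holds in this form: both parts of the secondary index depend on the 20% cut, both lose power by it, and item 7 conflicts with section 4 on who enters the correlation. Under the assumptions in the working, the split gives up about 36% to 51% of the information at 50% to 80% response. At r = 0.5 it lowers power from 0.78 to between 0.57 and 0.44, and the responder-only correlation does worse still at 50% and 70% response.

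The direction does not depend on the assumed correlation or response rate within the ranges tried; the size does. The figures also treat flora change as a single normally distributed measure, which the documents do not define. This should be changed, but it does not touch the main index.

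**What to change.** - Reconcile item 7 with section 4. State that the leading secondary analysis relates flora change to the continuous change in PANSS negative score in all treated patients, for each flora measure analysed.
- Use either the Pearson or Spearman correlation already listed, or a regression with baseline flora and baseline PANSS negative score as covariates, and name the choice in advance.
- Extend the immune-factor correlation to all treated patients.
- Keep the 20% effective/ineffective comparison as a supportive display, with the two group sizes shown.

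The cost is wording in item 7 and section 4; no patients, visits or assays are added. The downside is reliance on a roughly linear relation (or monotone, for Spearman), to be checked with a scatter plot. Covariates, if used, cost 2 degrees of freedom.

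### Flora correlations with symptoms and immune factors are limited to responders, which drops non-responders and selects on one of the correlated variables

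*Combined protocol and SAP*

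**What the plan says.** Section 3, item 7 (effectiveness evaluation index) sets out three things.

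- The main index compares flora change between patients and controls: "The main evaluation index is the difference between the change of the intestinal microbial flora of the study group and the control group".
- A responder definition: "the secondary evaluation index is the PANSS negative symptom scale score reduction rate $\geq 20\%$ as the effective group". Section 2 uses the same threshold: "a 20% reduction rate for amisulpride treatment of negative symptoms is taken as the effective response".
- Two secondary analyses that use this definition. The first compares both classes of patient: "observe the effective group and the ineffective group The difference in the changes of the intestinal microflora of the group". The second names only one class: "the correlation between the changes of the intestinal microflora of the effective group and immune factors and negative symptoms".

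Section 4 gives the method without saying who is analysed: "changes in immune factors and changes in intestinal flora composition were analyzed by PEARSON or SPEARMAN", with change in negative symptoms listed alongside. No other part of the document gives a population for the correlations.

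Stool (Section 3, item 2), blood (item 4) and PANSS (item 5) are scheduled for every treated patient at baseline and weeks 2, 4 and 8.

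**The concern.** The title asks how gut flora relate to negative symptoms. The correlation in item 7 is the only planned analysis that sets the amount of flora change against the amount of symptom change. The one population the plan states for it is formed after baseline by a cut on symptom change, which is one of the two variables being correlated.

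Two effects follow. First, non-responders leave the correlation and an already small sample shrinks. Second, the range of symptom change is truncated. If the slope is the same in responders and non-responders, and symptom change is roughly normal, truncation also pulls the coefficient towards zero. A weak or null result could then come from the selection and not from the biology.

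The effective versus ineffective comparison does use non-responders, but it reduces response to two classes and so does not replace a continuous correlation. For the flora-immune correlations only the first effect is sure to apply.

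**Working it through.** **Inputs from the plan.** 30 patients enrolled and 10% dropout (Section 2: "According to 10% dropout, about 30 samples from the study group"), so 30 × 0.9 = 27 evaluable; two-sided 0.05 (Section 2); response means a reduction of at least 20% (item 7).

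**Assumed, because the plan gives no figure.** Responder share 50% or 80%; true correlation 0.5 in all patients; one Pearson test; the same slope in responders and non-responders.

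**The plan's own figure.** The 26 in Section 2 reproduces as the per-group size of a two-sample t-test with effect size 0.8, two-sided 0.05 (power 0.807). Then 26 / 0.9 = 28.9, or about 30. It is not a power calculation for the correlation, and the plan has none.

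**Step 1: smaller sample only.** Fisher approximation: power ≈ Φ(atanh(r)·√(n − 3) − 1.96), with atanh(0.5) = 0.549.

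- All 27: 0.549 × 4.899 − 1.96 = 0.73, power 77%.
- 50% share, 13.5 patients, rounded to 14: 0.549 × 3.317 − 1.96 = −0.14, power about 45%.
- 80% share, 21.6 patients, rounded to 22: 0.549 × 4.359 − 1.96 = 0.43, power 67%.

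The correlation detectable with 80% power, tanh(2.802 / √(n − 3)), rises from 0.52 (n = 27) to 0.69 (n = 14) or 0.57 (n = 22).

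**Step 2: truncation, normal symptom change.** Suppose the correlated change is the same percentage reduction that defines response. With a = z(1 − share) and λ = φ(a)/share, the variance left among responders is v = 1 + aλ − λ², and the responder correlation is ρ√v / √(ρ²v + 1 − ρ²).

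- 50%: a = 0, λ = 0.798, v = 0.363, r = 0.33.
- 80%: a = −0.842, λ = 0.350, v = 0.583, r = 0.40.

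**Step 3: both effects, other shapes.** Simulated trials of 27 patients, with flora change = 0.5 × standardised symptom change + √0.75 × normal noise. The random subset has the same expected size as the effective group, so it shows the loss from sample size alone.

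| Symptom change | Share | r in responders | Power, all | Power, random subset | Power, effective group |
|---|---|---|---|---|---|
| Normal | 50% | 0.33 | 78% | 45% | 20% |
| Normal | 80% | 0.40 | 78% | 68% | 47% |
| Right-skewed (gamma, shape 4) | 50% | 0.43 | 77% | 44% | 32% |
| Right-skewed (gamma, shape 4) | 80% | 0.46 | 77% | 67% | 58% |
| Exponential | 50% | 0.50 | 73% | 42% | 42% |
| Exponential | 80% | 0.50 | 73% | 63% | 63% |
| Left-skewed (mirrored gamma) | 50% | 0.22 | 77% | 44% | 11% |
| Left-skewed (mirrored gamma) | 80% | 0.33 | 77% | 66% | 32% |

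The loss runs from 73 − 42 = 31 to 77 − 11 = 66 points at a 50% share, and from 73 − 63 = 10 to 77 − 32 = 45 points at 80%. Exponential change shows no shrinkage of r, so all of its loss comes from the smaller sample.

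**Step 4: correlated change not identical to the percentage reduction.** The plan does not say that the correlated change is a percentage. If the two correlate at 0.9 (normal case), responder r is 0.37 or 0.42 and power 25% or 52% at the two shares. At 0.8 they are 0.41 or 0.44 and 30% or 55%.

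**Step 5: slopes that differ by response.** Normal change, responder slope 0.5, lines meeting at the threshold.

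| Non-responder slope | Share | Power, all | Power, effective group |
|---|---|---|---|
| 0 | 50% | 29% | 20% |
| 0 | 80% | 60% | 47% |
| −0.5 | 50% | 7% | 21% |
| −0.5 | 80% | 39% | 47% |

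**The case against.** **Section 4 is silent, and silence may mean all patients.** That reading is possible, and item 7 is loosely worded. But item 7 names both classes for the comparison and one for the correlation, so restriction is the natural reading. If Section 4 was meant to include everyone, the two sections disagree and the population could be chosen after the results are seen. The same edit cures both.

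**The size rests on assumptions.** True. Responder share, true correlation, slope and shape all come from outside the documents, and the largest losses need left-skewed change, which nothing in the plan supports. The figures are illustrations. The direction is the same in every common-slope case.

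**A responder-only correlation may be intended, because flora may track improvement only where the drug works.** This is the strongest point. In that case the responder correlation is a different quantity, not an understated one. With a flat non-responder slope the advantage of using everyone narrows to 29% against 20% (50% share) or 60% against 47% (80% share). With opposite slopes it reverses. The plan gives no such rationale, and the fix keeps the responder-only analysis.

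**The all-patient analysis is weak too.** Also true. At a true correlation of 0.3 (normal) one test has 34% power in all patients, against 9% or 18% in responders. With a Bonferroni correction over an assumed 20 tests, all-patient power at 0.5 is about 36%. Including everyone helps but does not make the analysis strong.

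**It is secondary and the data are not lost.** Correct, and this limits how serious the point is.

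**Conclusion.** The concern holds. The only population the plan states for these correlations excludes non-responders and selects on one of the correlated variables, although all treated patients are measured. For flora against symptom change, with 27 evaluable patients, a true correlation of 0.5 and a common slope, power for a single test drops by 31 to 66 points if half respond and by 10 to 45 points if 80% respond. In the normal case that is from 78% to 20% or 47%. Using all patients remains better with a flat non-responder slope and loses only in the opposite-slope case computed. For flora against immune factors the sample is smaller and the result applies to responders only; no power figure is claimed. The main index does not change. This should be corrected, but it does not threaten the trial's primary comparison.

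**What to change.** In Section 3, item 7, state that the correlations of flora change with immune-factor change and with negative-symptom change are calculated in all treated patients with paired data, with PANSS negative change kept continuous. Repeat that population in Section 4 next to the Pearson or Spearman method. Keep the effective-group-only correlation, labelled exploratory, and leave the effective versus ineffective comparison as planned.

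The cost is one sentence in each section, with no added patients, visits or assays. The only thing given up is that the responder-only correlation becomes exploratory.

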Study on the Gut Microbial Mechanism of
Negative Symptoms of Schizophrenia

Aug. 25th,2020

1. Subjects

Recruit 30 outpatient/inpatient schizophrenia patients (dominant negative symptoms) in Shanghai Mental Health Center (research group). At the same time, 15 cases of normal healthy people (control group) with similar eating habits and ages in the same region were matched.

Inclusion criteria:

- 1) 18-45 years old, Han nationality, no gender limit;
- 2) Meet the diagnostic criteria of "Schizophrenia" in the American Diagnostic 3) Standards for Mental Disorders (DSM-V);
- 3) The first attack, no antipsychotic drugs have been used in the past six months;
- 4) The PANSS negative symptom subscale has at least 3 items with 4 points and above or at least two items with 5 points and above, and the positive symptoms score is less than 19 points;
- 5) The negative symptom score is at least 6 points or more higher than the positive symptom score;
- 6) The cultural, social and educational background is sufficient to understand informed consent and research content.

Exclusion criteria:

- 1) Combined with DSM-V diagnosis other than schizophrenia;
- 2) G6 \geq 4 points in PANSS, or CDSS \geq 6 points;
- 3) SAS Side Reaction Scale $>$ 3 points;
- 4) Organic diseases of the central nervous system;
- 5) In the past two months, there were people who were dependent or abused on alcohol or other substances, which caused significant impairment of social and cognitive function;
- 6) In the past year, there have been major life events such as widowhood;

- 7) Serious suicide attempts;
- 8) The current patient's severe and unstable physical disease;
- 9) Pregnant and lactating women;
- 10) Have a history of antibiotic use of more than 3 days within 3 months;
- 11) Use probiotics (lactic acid products, etc.) for more than 3 days within 3 months;
- 12) Type 1 diabetes and severe diabetes complications;
- 13) Digestive system diseases such as gastrointestinal inflammation, acute or chronic hepatitis;
- 14) Severe organ diseases, such as cancer, coronary heart disease, myocardial infarction, cerebral hemorrhage;
- 15) Have infectious diseases, such as tuberculosis, AIDS;
- 16) Drug treatment of cholecystitis, peptic ulcer, urinary tract infection, acute nephritis, cystitis or hyperthyroidism.

Withdrawal criteria: Anyone who meets any of the following conditions at any time will terminate the study and complete all the evaluations originally scheduled for the 8th weekend:

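### The baseline patient-control comparison uses an equal-variance one-way ANOVA on 30 v 15, so its error rate moves away from 5% if the groups differ in spread; Welch's test is a nearly free replacement

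*Combined protocol and SAP*

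**What the plan says.** Section 4 (Statistical analysis) gives the method for comparing patients with controls in one sentence: "One-way analysis of variance was used to compare the two groups at baseline". No other patient-control test is named. The repeated-measures ANOVA in the same section is for the study group alone, and the correlations relate changes in symptoms, immune factors and flora to each other. Section 4 mentions no check of equal variances, no unequal-variance test, and no transformation or rank method for this comparison.

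The group sizes are unequal by design. Section 1 (Subjects) plans 30 patients and "15 cases of normal healthy people (control group) with similar eating habits and ages in the same region were matched". Section 2 (Calculation of sample size) repeats this: "about 30 samples from the study group and 15 samples from the healthy control group are matched".

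The only significance level is in section 2: "the first type of error α is 0.05", two-sided.

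The main evaluation index is in section 3, item 7. It is the patient-control difference in the change of the flora, and section 4 assigns it no test.

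**The concern.** One-way ANOVA on two groups gives F = t², where t is the equal-variance t statistic. Its standard error pools the two sample variances, weighted by degrees of freedom. With equal group sizes, unequal spread does little harm. With 30 v 15, the larger group dominates the pooled variance while the smaller group contributes most to the true uncertainty of the difference. The standard error is then too large if patients are the more variable group, and too small if controls are.

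The groups are not randomised and differ in health, so equal spread of flora measures and cytokines cannot be taken for granted. A baseline comparison of these measures is therefore a substantive comparison here and not a check on allocation. At stake are the p-values and confidence intervals from the one between-group test that the plan specifies.

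**Working it through.** **Inputs from the documents.** n₁ = 30 patients, n₂ = 15 controls (sections 1 and 2); two-sided α = 0.05 and effect size 0.8 (section 2); one-way ANOVA at baseline (section 4).

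**Assumed, because the documents do not give them.** The SD ratio between groups (shown from 1 to 2 in each direction), normal data, and independent groups. Controls are described as matched, but no matched structure is given for the analysis.

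**The plan's own figure.** Section 2 states a required size of 26. A two-sample equal-variance t test with d = 0.8, two-sided 0.05 and 1:1 allocation gives power 0.791 at 25 per group and 0.807 at 26 per group, so 26 is reproduced as a per-group figure. Allowing for 10% dropout, 26/0.9 = 28.9, or 29, stated as about 30. The plan gives no error rate for the 30 v 15 comparison, so there is nothing further to reproduce.

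**Formula.** With s₁ and s₂ the true SDs,

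- true variance of the difference: V = s₁²/n₁ + s₂²/n₂
- variance ANOVA assumes, on average: P = sₚ²(1/n₁ + 1/n₂), where sₚ² = (29s₁² + 14s₂²)/43 and 1/30 + 1/15 = 0.1
- k² = V/P, and the large-sample error is 2(1 − Φ(1.96/k))

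**Patient SD twice control SD** (s₁ = 2, s₂ = 1): V = 4/30 + 1/15 = 0.200; sₚ² = (116 + 14)/43 = 3.023; P = 0.302; k = √(0.200/0.302) = 0.813; 1.96/k = 2.41; error about 1.6%.

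**Control SD twice patient SD** (s₁ = 1, s₂ = 2): V = 1/30 + 4/15 = 0.300; sₚ² = (29 + 56)/43 = 1.977; P = 0.198; k = √(0.300/0.198) = 1.232; 1.96/k = 1.59; error about 11.2%.

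**Small-sample check by simulation** (1,000,000 normal samples per setting, nominal 5%):

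| More variable group | SD ratio | ANOVA | Welch |
|---|---|---|---|
| neither | 1 | 5.0% | 5.0% |
| patients | 1.25 | 3.5% | 5.0% |
| patients | 1.5 | 2.7% | 5.0% |
| patients | 2 | 1.8% | 5.0% |
| controls | 1.25 | 6.8% | 5.1% |
| controls | 1.5 | 8.5% | 5.0% |
| controls | 2 | 11.2% | 5.0% |

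**Cause.** With 22 v 22 and a two-fold ratio, ANOVA's error is 5.2% whichever group is more variable. The distortion therefore needs the unequal sizes and the unequal spread together.

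**Power, normal data.** With patient SD twice control SD and a true difference of 1.2 control SDs, power is 0.58 for ANOVA and 0.75 for Welch. With equal SDs and d = 0.8, it is 0.696 for ANOVA and about 0.685 for Welch.

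**Skewed data.** With lognormal-shaped data, equal means and control SD twice patient SD, analysed on the raw scale, the errors are:

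| Log-SD | ANOVA | Welch |
|---|---|---|
| 0.5 | 11.8% | 6.7% |
| 0.75 | 12.2% | 8.4% |
| 1.0 | 12.6% | 10.6% |

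At log-SD 1.0 and control SD 1.5 times patient SD, Welch (8.4%) is slightly worse than ANOVA (8.0%).

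**The case against.** **The premise is not in the documents.** This stands. No SD is reported for any measure. Some features favour similar spread: controls are matched on region, eating habits and age, and patients are narrowed by age limits, first episode, and the antibiotic, probiotic and digestive exclusions. At a ratio of 1.25 the error is only 3.5% or 6.8%. If patients are the more variable group, the test is conservative and the 11.2% does not arise. The claim is therefore conditional. Equally, nothing in the plan supports equal spread, and a test that does not need it is available.

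**It is only a baseline comparison.** This also stands. A reader might infer that the trial's main comparison runs at up to 11% error. The documents do not support that: the ANOVA sentence is limited to baseline, and the main index has no named test, which is a separate and larger gap.

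**Welch does not guarantee 5%.** Correct. The skewed-data figures show that it corrects unequal variance and not skewness. It is closer to 5% than ANOVA in nearly all settings tried, but the scale of analysis has to be chosen as well.

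**ANOVA is standard, and the analyst may check variances.** The plan does not forbid a check, but it does not provide for one. A preliminary Levene test is also a weak safeguard: at a 1.5-fold ratio with 30 v 15, it detects the inequality in only about 32-39% of simulated samples.

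**Conclusion.** The point holds for the baseline patient-control comparison, and conditionally on unequal spread. At 30 v 15, one-way ANOVA has an actual error of about 3.5% to 1.8% if patients are more variable by a factor of 1.25 to 2, and about 6.8% to 11.2% if controls are. These figures rest on normal, independent data and on assumed SD ratios. The arithmetic is firm; whether the SDs differ, and in which direction, is unknown from the documents.

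The documents do not show that the groups do differ in spread, that the main index is affected, or that Welch restores 5% for strongly skewed data on the raw scale. What remains is a named method with a better replacement that needs no larger sample: a cheap improvement.

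**What to change.** In section 4, replace one-way ANOVA for the baseline patient-control comparison by Welch's test, reported with its unequal-variance 95% interval. State that positive, right-skewed measures such as cytokines are analysed on the log scale, with results given as ratios of geometric means. The log does not apply directly to flora measures that can be zero, so the plan should say how those are handled.

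The plan names no test for the between-group difference in change. If the same two-group method is adopted there, use Welch there too. With 10% patient dropout (27 v 15), ANOVA's error at a two-fold SD ratio would still be 2.2% if patients are more variable and 10.3% if controls are.

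The cost is a sentence or two in section 4, no change to the sample size, and about 1 point of power if the SDs are equal (0.696 − 0.685 = 0.011 at d = 0.8). On the log scale the comparison is of geometric and not arithmetic means, and the report should say so.
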